4.6.2 Monitoring for and Management of Hepatobiliary Toxicity

Hepatobiliary toxicity has been reported with AAV gene therapy treatment ([Chan, 2020](#)) and in this study (ATX-MTM-002). In Study ATX-MTM-002, AT132-related SAEs involving the hepatobiliary system, including intrahepatic cholestasis, have occurred in subjects with XLMTM treated at the 1.0×10^{14} vg/kg and 3.0×10^{14} vg/kg dose levels. Subjects will be administered glucocorticoid prophylaxis and ursodiol prophylaxis as outlined in [Sections 4.4](#) and [4.5](#), respectively. Routine surveillance and evaluation of any signs or symptoms of hepatobiliary toxicity is an essential safety parameter. The primary monitoring strategy for identifying potential hepatobiliary toxicity will be through frequent, scheduled testing of the following LFTs: ALT, AST, gamma-glutamyltransferase (GGT), total bilirubin (TBL), and direct bilirubin. Additional monitoring will include scheduled liver ultrasound procedures and as of protocol v10 serum bile acid levels in order to better understand the long-term behavior of intrahepatic cholestasis in XLMTM subjects. The frequency of these assessments is outlined in the Schedule of Events ([Sections 5.4](#), [5.5](#), and [5.6](#)).

Site Investigators are responsible for prompt review of all laboratory or procedural results related to potential hepatobiliary toxicity. To enhance the monitoring and management of potential hepatotoxicity, sites will identify a site hepatologist (preferably with expertise in pediatric cholestatic disease). The site hepatologist will assist the study site and any managing physician responsible for patient care with interpretation of abnormal hepatobiliary test results and treatment. A high level of awareness and vigilance for potential hepatobiliary toxicity should be maintained in the setting of gene therapy clinical studies. Details related to the monitoring, diagnosis, and treatment of hepatobiliary toxicity are described herein. Any laboratory tests and/or procedures performed for these safety events should be reported in the eCRF.

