- ^{bb} Subjects will be administered a course of glucocorticoid therapy commencing Day -1 and continuing for a period of 16 weeks as a preventative measure for immune-mediated hepatic injury. For subjects weighing < 60 kg, the dose will be 1 mg/kg prednisolone orally daily for 8 weeks, then tapered down for 8 weeks per Investigator discretion. For subjects weighing ≥ 60 kg, the dose will be 60 mg prednisolone orally daily for 8 weeks, then tapered down for 8 weeks per Investigator discretion.
- ^{cc} Ursodiol to be dosed at 20 mg/kg/day (divided either BID or TID at the Investigator's discretion) to Week 12 and at the Investigator's discretion thereafter.
- ^{dd} Viral shedding will be assessed on samples of saliva (swab), stool, and urine (diaper collection or urine bag). Collection of each sample type will begin on Day 1 and will continue until each sample type has 3 consecutive data points at or below the limit of detection (BLOD). Sponsor will notify site when collection can cease. Not conducted at Week 10 or 14.
- ^{ee} Subjects in Germany will not have a wrist X-ray. After the Week 48 visit, wrist X-ray only needs to be performed annually thereafter (Month 24, Month 36). As of protocol v12, the wrist X-ray assessment will no longer be collected at Month 48 visit onward.
- ^{ff} As of protocol v12, these assessments will no longer be collected at Month 48 visit onward.

5.6 Schedule of Events for Subjects Treated with AT132: Month 72 (Year 6) – Month 120 (Year 10) (End of Study)

Study Phase/Visit	Month 72	Month 84	Month 96	Month 108	Month 120
Study Day	2190	2555	2920	3285	3650
Visit Window (days)	±60	±60	±60	±60	±60
Physical Examination ^a	X	X	X	X	X
Ventilator Dependence Questionnaire ^b	X	X	X	X	X
Samples for:	X	X	X	X	X
Safety labs (hematology) (central lab) ^{c,d}	X	X	X	X	X
Safety labs (chemistry) (central lab) ^{d,e,f,g} Comprehensive metabolic profile ALT, AST, Total and direct bilirubin, GGT Serum bile acids, total (fasting preferred) PTT and PT/INR Troponin I and T CK Alpha fetoprotein	X	X	X	X	X
Liver ultrasound (local) ^f	X	X	X	X	X
Motor milestone assessments ^h	X	X	X	X	X
ACEND	X	X	X	X	X
Clinical global impression scales ⁱ	X	X	X	X	X
Swallowing questionnaire	X	X	X	X	X
Secretions management assessment ^j	X	X	X	X	X
AEs/concomitant medications	X	X	X	X	X

NOTE: Long-term follow-up visits and/or assessments after the 5-year (Month 60) visit can be done remotely per discretion of investigator in consultation with Medical Monitor.

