4.6.2 Additional Safety Assessments

4.6.2.1 Clinical Laboratory Evaluation

The baseline value will be the last non-missing value taken prior to first dose of study drug.

Quantitative values evaluated by the central or local laboratory including hematology, serum chemistry, additional serum chemistry (includes complement panel, cytokine panel, and bile acids), coagulation, and urinalysis will be summarized using mean, standard deviation,

minimum, maximum and median by treatment group at each analysis visit. Additionally, a within-participant change will be calculated as the post-baseline measurement minus the baseline measurement and summarized in the same way. Each laboratory result will be classified as low (L), normal (N), or high (H) at each visit according to the laboratory supplied reference ranges.

Central lab results should be summarized if they're available at an analysis visit. If both local and central laboratory results are available at an analysis visit, the central lab values should be used preferentially for analysis. If only local labs are available at an analysis visit but central lab values are missing, then local labs may be used for analysis.

The number and percentage of participants below and above the reference range will be summarized for each dose level and overall at each visit.

Frequency tabulations of qualitative clinical laboratory variables (urinalysis) will be presented for each treatment group at each visit.

Selected laboratory abnormalities will be evaluated based on pre-specified threshold level (potentially clinically significant [PCS]) criteria. If both the baseline and on-treatment values of a parameter are beyond the same threshold limit for that parameter, then the on-treatment value will be considered a PCS value only if it is more extreme (farther from the limit) than was the baseline value. If the baseline value for a parameter is missing and the on-treatment value of a parameter is beyond the PCS limit, then the on-treatment value will be considered a PCS value. The pre-defined criteria for PCS laboratory values are presented below.

Table 4 Potentially Clinically Significant Laboratory Values

Pre-specified Threshold Values for Selected Laboratory Tests (Potentially Clinically Significant Laboratory Criteria)	
Laboratory Parameter	Pre-Specified Level
Chemistry	
Sodium	<132 mEq/L
Potassium	<3.0, <3.5, >5.0, >6.0 mEq/L
Serum bicarbonate	<10, <12, >30, >32 mEq/L
Creatinine	>25% increase from baseline

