CK	>25% increase from baseline
ALT	>25% increase from baseline or 5 x ULN
AST	>25% increase from baseline or 5 x ULN
Glucose	>250 mg/dL
Troponin T and troponin I	>25% increase from baseline
Hematology	
Hemoglobin	<9 g/dL
Hematocrit	<27%

For each laboratory threshold criterion, the number and percent of participants who have a laboratory value meeting the threshold criteria during the investigational period will be summarized by dose level group and visit.

Laboratory results will be graded using NCI-CTCAE v4.03 or higher, where possible. NCI-CTCAE grade of laboratory evaluations will be summarized by number and percentage of participants at each visit.

The number and percentage of participants with \geq Grade 1 shift from baseline in laboratory test result will be summarized by dose level and laboratory parameter.

The following data may be presented graphically by treatment group:

- Laboratory test results using box plot (by visits within each period),
- Change from baseline in laboratory test results using box plot (by visits within each period),
- Laboratory test results using spaghetti plot.

All laboratory results will be listed. Laboratory results that are above or below normal limits will be flagged, along with clinical significance, in the listings. In addition, laboratory results that meet or exceed the pre-specified levels (i.e., are above [or below as appropriate] the pre-specified levels as shown in the above [table](#)) will be flagged.

Should local laboratory values be collected, they will be listed and out of range values will be flagged.

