4.10.2 Analysis Windows

The data summary by visits will be done following the analysis windows specified in the [tables](#) below:

Table 9 Analysis Visit Windows for Efficacy Endpoints

Analysis Visits	Scheduled Day in Protocol (Day)	Analysis Windows (Day)								
		(a) Ventilator param., MIP, MEP, P0.1, tidal volume, ventilator weaning & discont.	(b) Secretion manage. assessment (PGIS-S, PGIS-I)	(c) Motor develop. milestone,	(d) Bayley-III, motor domain	(e) CHOP INTEND, MFM-32	(f) ACEND	(g) PedsQL	(h) Clinical global impression scales, Swallowing questionnaire, Communicative development inventories	(i) Ventilator Depend. Question.
Baseline	-1	≤ -1	≤ -1	≤ -1	≤ -1	≤ -1	≤ -1	≤ -1	≤ -1	≤ -1
Dosing	1									
Day 2	2									
Day 3	3									
Week 1	7						1-10	1-10	1-10	1-17
Week 2	14	1-21				1-21	11-21	11-21	11-21	
Week 3	21									
Week 4	28	22-56	1-42	1-56	1-56	22-42	22-56	22-56	22-42	18-56
Week 5	35									
Week 6	42									
Week 7	49									
Week 8	56		43-70			43-70			43-70	
Week 9	63									
Week 10	70									
Week 11	77									
Week 12	84	57-98	71-98	57-98	57-98	71-98	57-98	57-98	71-98	57-98
Week 13	91									
Week 14	98									
Week 15	105									
Week 16	112	99-140	99-126	99-140	99-140	99-140	99-140	99-140	99-140	99-140
Week 20	140		127-154							
Week 24	168	141-252	155-182	141-210	141-210	141-210	141-210	141-210	141-210	141-182
Week 28	196		183-210							183-210
Week 32	224		211-238							211-238
Week 36	252		239-266	211-294	211-294	211-294	211-294	211-294	211-294	239-266
Week 40	280		267-294							267-294
Week 44	308		295-322							295-322
Week 48	336	253-442	323-442	295-396	295-396	295-442	295-442	295-442	295-442	323-396
Month 15	456			397-502	397-502					397-502
Month 18	548	443-639	443-639	503-639	503-639	443-639	443-639	443-639	443-639	503-639

Analysis Visits	Scheduled Day in Protocol (Day)	Analysis Windows (Day)								
		(a) Ventilator param., MIP, MEP, P0.1, tidal volume, ventilator weaning & discount.	(b) Secretion manage. assessment (PGIS-S, PGIS-I)	(c) Motor develop. milestone,	(d) Bayley-III, motor domain	(e) CHOP INTEND, MFM-32	(f) ACEND	(g) PedsQL	(h) Clinical global impression scales, Swallowing questionnaire, Communicative development inventories	(i) Ventilator Depend. Question.
Month 24	730	640-821	640-821	640-821	640-821	640-821	640-821	640-821	640-821	640-821
Month 30	[contact]	822-1004	822-1004	822-1004	822-1004	822-1004	822-1004	822-1004	822-1004

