Month 36	1095	1005-1186	1005-1186	1005-1186	1005-1186	1005-1186	1005-1186	1005-1186	1005-1186	1005-1186
Month 42	1278	1187-1369	1187-1369	1187-1369	1187-1369	1187-1369	1187-1369	1187-1369	1187-1369	1187-1369
Month 48	1460	1370-1551	1370-1551	1370-1551	1370-1551	1370-1551	1370-1551	1370-1551	1370-1551	1370-1551
Month 54	1643	1552-1734	1552-1734	1552-1734	1552-1734	1552-1734	1552-1734	1552-1734	1552-1734	1552-1734
Month 60	1825	≥1735	≥1735	1735-2007	≥1735	≥1735	1735-2007	≥1735	≥1735	1735-2007
Month 72	2190			2008-2372			2008-2372			2008-2372
Month 84	2555			2373-2737			2373-2737			2373-2737
Month 96	2920			2738-3102			2738-3102			2738-3102
Month 108	3285			3103-3467			3103-3467			3103-3467
Month 120	3650			≥3468			≥3468			≥3468

Abbreviations: NA = Not Applicable.
 Grey area indicates NA.

Table 10 Analysis Visit Windows for Safety Endpoints

Analysis Visits	Scheduled Day in Protocol (Day)	Analysis Windows (Day)												
		(a) LFTs, CK (including CK isoenzymes), CRP, serum bicarbonate (local & central)	(b) Chemistry excluding (a), hematology (local & central)	(c) Urinalysis (local & central)	(d) Cytokine panel, complement panel (central)	(e) Troponin T and/or I (local & central)	(f) Coagulation (local)	(g) Viral Shedding (central)	(h) Serum bile acid (central)	(i) Platelet monitoring	(i) Vital signs	(j) 12-Lead ECG	(k) Liver ultrasound	(l) Anti-AAV8, Anti-MTM1 (central)
Baseline	-1	≤ -1	≤ -1	≤ -1	≤ -1 [#]	≤ -1	≤ -1		≤ -1	≤ -1	≤ 1*	≤ -1	≤ -1	
Dosing	1							1			1*			
Day 2	2	1-4	1-4	1-4		1-4		2		1-4	2	1-4		
Day 3	3				1-5			3-5			3-5			
Wk 1	7	5-10	5-10	5-10	6-10	5-10	1-17	6-14		5-10	6-10	5-10		
Wk 2	14	11-17	11-21	11-21	11-17	11-17				≥11	11-21	11-21		
Wk 3	21	18-24			18-24	18-24		15-28						
Wk 4	28	25-31	22-42	22-42	25-31	25-35	18-42				22-42	22-42	1-56	1-35
Wk 5	35	32-38			32-38			29-42						
Wk 6	42	39-45			39-45	36-49								36-49
Wk 7	49	46-52			46-52			43-56						
Wk 8	56	53-59	43-70	43-59	53-59	50-59	43-112				43-70	43-70		50-70
Wk 9	63	60-66		60-66	60-66	60-66		57-70						
Wk 10	70	67-73		67-73	67-73	67-73								
Wk 11	77	74-80		74-80	74-80	74-80		71-84						
Wk 12	84	81-87	71-98	81-98	81-87	81-87			1-126		71-98	71-98	57-98	71-98
Wk 13	91	88-94			88-94	88-94		85-98						
Wk 14	98	95-101			95-101	95-101								
Wk 15	105	102-108			102-108	102-108		99-136						
Wk 16	112	109-140	99-140	99-140	109-140	109-140					99-140	99-140	99-140	99-140
Wk 24	168	141-210	141-210	141-210	141-210	141-210	113-210	137-210	127-210		141-210	141-210	141-210	141-210

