@Only Applicable to Serum Bile Acid, Total.

Table 11 Analysis Week Window for Weekly Average Hours of Ventilator Support from Diary of Ventilator Dependence

Analysis Week	Analysis Windows (Day)
Baseline	-7 - -1
Week 1	1 - 7
Week 2	8 - 14
Week 3	15 - 21
Week 4	22 - 28
Week 5	29 - 35
Week 6	36 - 42
Week 7	43 - 49
Week 8	50 - 56
Week 9	57 - 63
Week 10	64 - 70
Week 11	71 - 77
Week 12	78 - 84
Week 13	85 - 91
Week 14	92 - 98
Week 15	99 - 105
Week 16	106 - 112
Week 17	113 - 119
Week 18	120 - 126
Week 19	127 - 133
Week 20	134 - 140
Week 21	141 - 147
Week 22	148 - 154
Week 23	155 - 161
Week 24	162 - 168
Week 25	169 - 175
Week 26	176 - 182
Week 27	183 - 189
Week 28	190 - 196
Week 29	197 - 203
Week 30	204 - 210
Week 31	211 - 217
Week 32	218 - 224
Week 33	225 - 231
Week 34	232 - 238
Week 35	239 - 245
Week 36	246 - 252
Week 37	253 - 259
Week 38	260 - 266
Week 39	267 - 273
Week 40	274 - 280
Week 41	281 - 287
Week 42	288 - 294
Week 43	295 - 301
Week 44	302 - 308
Week 45	309 - 315
Week 46	316 - 322
Week 47	323 - 329
Week 48	330 - 336

If more than one observation exists within the analysis window, the observation closest to the scheduled visit day will be selected for that visit. If there are two observations that have the same distance from the scheduled day, the value that is after the scheduled day will be

selected in the analysis. If more than one observation is made on the same day, an average value if continuous or the worst value if categorical will be included in the analysis.

The Follow Up visit will include all data collected beyond 10 days after the last dose of study drug. If there is more than one value, then the value that is closest to day 28 from the last dose of study drug will be selected for the analysis. The same logic will be applied as above for more than one value.

If a table summary for visits is not planned, then visit windowing does not need to be done for that data.

For diary data, results will be mapped to a particular visit week by the following logic, which is the same as in [Table 11](#):

```
avisit="Week "||strip(put(ceil(ady/7),best.))
```

Per protocol, daily diary collection should end after Week 48. However, for some participants it continued longer. For daily diary analysis visits that correspond to a “Month X” official analysis visit name, the avisit calculation above will be converted to the corresponding Month X official analysis according to the analysis windows table.

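### SAP Table 10 gives liver function tests and coagulation an open-ended Month 60 window and no Month 72–120 windows, so scheduled Year 6–10 results drop out of the by-visit laboratory tables or are mislabelled

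*SAP*

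**What the plan says.** Protocol 5.6 has one chemistry cell, marked for Months 72, 84, 96, 108 and 120 (Days 2190, 2555, 2920, 3285 and 3650, each ±60 days), which includes "Comprehensive metabolic profile ALT, AST, Total and direct bilirubin, GGT Serum bile acids, total (fasting preferred) PTT and PT/INR Troponin I and T CK". Protocol 4.6.2 makes clear that GGT is one of the liver function tests: "scheduled testing of the following LFTs: ALT, AST, gamma-glutamyltransferase (GGT), total bilirubin (TBL), and direct bilirubin".

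SAP 4.10.2 makes the windows binding for tables by visit: "The data summary by visits will be done following the analysis windows specified in the" tables that follow. Table 10 column (a) is headed "LFTs, CK (including CK isoenzymes), CRP, serum bicarbonate (local & central"), and column (f) is coagulation. Both have Month 60 as Day 1735 or later and nothing for Months 72 to 120; the table note says grey cells are not applicable. Column (b), which is chemistry other than the tests in (a) plus hematology, and column (k), liver ultrasound, instead close Month 60 at Day 2007 and carry separate Month 72–120 windows. Bile acids also have Month 72–120 windows, with the footnote "Only Applicable to Serum Bile Acid, Total". When several results share a window, "If more than one observation exists within the analysis window, the observation closest to the scheduled visit day will be selected for that visit".

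SAP 4.6.2.1 plans descriptive statistics by analysis visit and two further by-visit tables: "The number and percentage of participants below and above the reference range will be summarized for each dose level and overall at each visit", and "NCI-CTCAE grade of laboratory evaluations will be summarized by number and percentage of participants at each visit". SAP 4.6.2.2 adds a by-visit table of liver-test thresholds.

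**The concern.** The protocol collects these tests for ten years, but the windowing rule has nowhere to put the second five years. An open-ended last window combined with a keep-the-closest rule does not leave late values unassigned. It assigns them to Month 60 and then drops them, or reports one of them as if it had been taken at Month 60.

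This matters because of what the tests are for. Protocol 1.5 reports four deaths with hepatobiliary failure among the causes, and says long-term follow-up is important for understanding such events. By-visit tables by dose level would carry liver ultrasound, total bile acids and hematology to Month 120, while liver function tests and coagulation would end at Month 60.

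**Working it through.** **Inputs.** Scheduled days and visit windows: Protocol 5.5 (Month 54 = Day 1643; Month 60 = Day 1825 ±14) and 5.6 (Months 72–120, ±60). Window cells: SAP Table 10. Selection rule: SAP 4.10.2.

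**Reproducing the SAP's own boundaries.** The midpoints between adjacent scheduled days are:

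- (1643 + 1825)/2 = 1734.0
- (1825 + 2190)/2 = 2007.5
- (2190 + 2555)/2 = 2372.5
- (2555 + 2920)/2 = 2737.5
- (2920 + 3285)/2 = 3102.5
- (3285 + 3650)/2 = 3467.5

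These give 1735–2007, 2008–2372, 2373–2737, 2738–3102, 3103–3467 and ≥3468, exactly as printed in column (k). The closed windows are therefore the table's general construction, and columns (a) and (f) depart from it.

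**Applying columns (a) and (f) as written.**

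| Visit | Allowed days | Window assigned | Days after Day 1825 |
|---|---|---|---|
| Month 60 | 1811–1839 | Month 60 | within 14 either way |
| Month 72 | 2130–2250 | Month 60 | 305–425 |
| Month 84 | 2495–2615 | Month 60 | 670–790 |
| Month 96 | 2860–2980 | Month 60 | 1035–1155 |
| Month 108 | 3225–3345 | Month 60 | 1400–1520 |
| Month 120 | 3590–3710 | Month 60 | 1765–1885 |

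- Month 60 present: it is always closest, so 5 of 5 later results are dropped.
- Month 60 missing: the Month 72 result is selected and labelled Month 60, and the other 4 are dropped.

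**Applying the closed windows instead.** Every visit, at any day within ±60, falls in its own window and all five results are kept.

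**Share of the schedule.** Column (a) has 1 (Day 2) + 16 (Weeks 1–16) + 3 (Weeks 24, 36, 48) + 8 (Months 18–60) = 28 post-dose rows; 5/(28 + 5) = 15%. Column (f) has 6 + 8 = 14; 5/(14 + 5) = 26%. These are counts of table rows, not of information.

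**Participant-visits (illustrative).** The documents do not give the number in Year 6–10 follow-up or their attendance. Dosed participants: 6 + 17 (Protocol 1.4.2, July 2020) + 1 (three undosed controls, of whom SAP 1.3 says two were never dosed) = 24, or up to 26 if both were replaced. Less four reported deaths, that is 20–22. Assuming 15–22 in follow-up and 50–100% attendance: 15 × 5 × 0.5 = 37.5 and 22 × 5 × 1.0 = 110, so about 38–110 participant-visits per test.

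**Is it only a version lag?** Protocol v12 is dated 17 May 2024 and SAP v4.0 was approved on 15 April 2024. The v12 change log marks troponin and CK as additions to the Month 72–120 block, but not liver function tests or PTT and PT/INR. SAP v4.0 already windows total bile acids, which sit in the same protocol cell. The timing does not explain the liver-test and coagulation gap. For CK (column a) and troponin (column e), the same gap is an update that v12 now requires, not an error in the SAP at its date.

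**The case against.** **The late data are not lost.** This stands in part. All results are listed. The table of shifts of at least Grade 1 is by parameter. Line plots cover ALT, AST, total and direct bilirubin, CK and Troponin T. Liver maxima are reported by period, including after Week 48 to end of study. Adverse-event summaries use the same periods, and Protocol 6.3.1 makes worsened Grade 3–4 laboratory results adverse events unless a reported diagnosis covers them. But the period maxima pool everything after Week 48 and cannot show timing or trend. GGT and the coagulation tests are in neither SAP Table 5 nor the required line plots, and SAP 4.6.2.2 does not name them among its liver parameters of interest.

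**Coagulation could be read into column (b).** Protocol 5.6 lists PTT and PT/INR in the chemistry row as central-laboratory tests, while column (f) is labelled local. This is a fair reading problem but not a way out. Protocol Appendix 1 and SAP 4.6.2.1 treat coagulation as its own panel. Column (f) also already windows Week 24 to Month 60, when Protocol 5.5 has coagulation at the central laboratory. Liver function tests have no such ambiguity, because column (b) excludes what is in (a).

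**Some affected tables are uncertain.** The by-visit liver-threshold sentence follows sentences limited to a 24-week period and may share that limit. The potentially-clinically-significant table depends on an investigational period whose meaning is unclear there. The descriptive, reference-range and CTCAE by-visit tables are affected either way.

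**The analysis is descriptive and time remains.** Both are true. They limit the consequence and make the correction cheap, but do not make the rule right.

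**Conclusion.** The concern holds: the windows are wrong as written for liver function tests and coagulation. After Month 60, 5 of 5 scheduled visits have no row. Each participant loses up to five results per test from the by-visit tables and, if Month 60 was missed, has a value taken 305–425 days late shown as Month 60, against a protocol window of ±14 days.

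That result rests only on the printed windows, the selection rule and visits attended within their protocol windows. The figure of 38–110 participant-visits rests on assumed numbers and attendance. The effect is confined to descriptive late-safety tables; the Week 24 primary analysis is not affected. It should be fixed, given the safety risk concerned and how little the fix costs.

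**What to change.** In SAP Table 10, columns (a) and (f), change Month 60 to 1735–2007 and add 2008–2372, 2373–2737, 2738–3102, 3103–3467 and ≥3468 for Months 72, 84, 96, 108 and 120, for the tests still scheduled. Use column (k) as the model rather than the bile-acid column (h), whose Month 60 cell reads as ≥1735 and so overlaps its own later windows; check that cell too. Drop or correct the local label on column (f).

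In the same update, bring the tables into line with protocol v12: give CK in column (a) and troponin in column (e) the same late windows, and extend the secretion-management column and the global-impression and swallowing parts of Table 9.

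The cost is SAP table edits and the matching programming. No new data are needed, because the assessments are already scheduled. SAP 1.2 places the final lock after all participants complete the study, so the change can be made in time.

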6.5.2 Management of Potential Immune Responses

Elevations of hepatic transaminases, CK, and troponin I, likely representing an immune response to the study treatment, have been reported in Study ATX-MTM-002 and are considered identified risks associated with AT132 administration. Refer to the Investigator's Brochure for details.

Guidelines for monitoring and management of such events are provided in [Section 4.6](#). Appropriate care for an individual subject will be determined by the Investigator based on an assessment of the subject's overall medical status. Corticosteroid treatment typically resolves the elevation of liver transaminases. However, when adverse events related to the immune response are of significant concern (eg, rAAV vector dose 1×10^{14} vg/kg and/or a transgene-mediated immune response), immunomodulation may include medications such as rapamycin (sirolimus), mycophenolate mofetil, calcineurin inhibitors (eg, cyclosporine, tacrolimus), and rituximab ([Prasad, 2022](#)).

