4.2.6 Glucocorticoid Administration

Concomitant glucocorticoid administration will be summarized by AT132 dose level and overall for the SAF. Glucocorticoids will be identified by ATCr_CD = "H02AB".

The glucocorticoid administration summary will include a summary table of:

- Duration of Taper
- Total days on protocol-specified glucocorticoid dose regimen (For subjects weighing < 60 kg, the dose will be 1 mg/kg prednisolone orally daily and for subjects weighing ≥ 60 kg, the dose will be 60 mg prednisolone orally daily) prior to taper (day prior to taper start date – Day -1 date + 1),

The day of taper start for a participant is defined as the date of first glucocorticoid record in the concomitant medication dataset where (frequency)*(dose) is less than the (frequency)*(dose) value for the initial glucocorticoid record in the dataset.

A listing of all subjects' glucocorticoid administration will be provided.

Individual subject line plots of ALT x ULN, AST x ULN, Total Bilirubin x ULN, Direct Bilirubin x ULN, CK x ULN, serum bile acid x ULN, and Troponin T x ULN will be created, with a dashed vertical line indicating where the taper began.

A swimmer plot may be created to visualize the glucocorticoid administration progression.

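### By-visit laboratory grade, out-of-range and ECG-criteria tables keep one nearest-day value per window, so off-schedule peaks go uncounted; a worst post-baseline row is needed

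*SAP*

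**What the plan says.** SAP 4.10.2 sets the selection rule for tables by visit: "If more than one observation exists within the analysis window, the observation closest to the scheduled visit day will be selected for that visit". Ties go to the later value; same-day values are averaged if continuous and taken at their worst if categorical. The rule is confined to by-visit tables: "If a table summary for visits is not planned, then visit windowing does not need to be done for that data".

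SAP 4.6.2.1 adds a source rule for laboratory data: "If both local and central laboratory results are available at an analysis visit, the central lab values should be used preferentially for analysis".

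Three sets of safety frequency tables are by visit and so inherit the nearest-day rule:
- counts below and above the reference range (SAP 4.6.2.1);
- CTCAE grade: "NCI-CTCAE grade of laboratory evaluations will be summarized by number and percentage of participants at each visit" (SAP 4.6.2.1);
- ECG criteria for heart rate, PR and QTc, by visit and time point (SAP 4.6.2.4).

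Two other domains have a peak rule. SAP 4.6.2.2 takes the highest post-dose liver test value per period from central and local laboratories. SAP 4.6.2.3 uses the highest and lowest vital sign for each participant.

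The individual line plots in SAP 4.2.6 cover liver tests and CK, then "serum bile acid x ULN, and Troponin T x ULN will be created". Protocol 6.5.2 names the other troponin: "Elevations of hepatic transaminases, CK, and troponin I, likely representing an immune response to the study treatment".

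**The concern.** Nearest-day selection suits a mean at a visit, because it keeps timing comparable across children. It does not suit a table meant to show how bad a value became. Protocol 5.1.1.8 expects extra laboratory tests when clinically indicated, and such tests need not fall near a scheduled day. After Week 16 the same section recommends the central laboratory for scheduled samples, so a local result can be displaced by a central one in the same window whatever its day.

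Protocol 1.5 lists myocardial events with troponin rises, acute and chronic CK elevation, and thrombocytopenia as identified risks. It also describes one child whose troponin rose when immunosuppression was withdrawn after more than 3 years, a time when the Table 10 windows last 182 or 183 days. At stake is a downward bias in the by-visit tables that describe these risks.

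**Working it through.** **Inputs.** Window limits and scheduled days come from SAP Table 10; visit tolerances come from the Protocol 5.4 and 5.5 schedules.

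**Reproducing the limits.** Each window ends at the midpoint between adjacent scheduled days, rounded down. Examples: (168 + 252)/2 = 210 and (336 + 548)/2 = 442. All limits checked match (troponin from Day 2 to Month 24; chemistry/hematology and ECG from Day 2 to Month 18).

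**Days on which an unscheduled value must lose.** Let a window run from day s to day e, with scheduled day c and visit tolerance w. Its length is L = e - s + 1. If the scheduled sample is on time, it lies within w days of c. Any unscheduled value more than w days from c is then farther away and is dropped. The number of such days is L minus the days of [c - w, c + w] that lie inside the window.

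| Window | Tests | Days | c | w | L | Must lose |
|---|---|---|---|---|---|---|
| Week 2 | CK, troponin | 11-17 | 14 | 3 | 7 | 7 - 7 = 0 |
| Week 4 | troponin | 25-35 | 28 | 3 | 11 | 11 - 7 = 4 |
| Week 4 | creatinine, platelets, ECG | 22-42 | 28 | 3 | 21 | 21 - 7 = 14 |
| Week 8 | creatinine, platelets, ECG | 43-70 | 56 | 3 | 28 | 28 - 7 = 21 |
| Week 12 | creatinine, platelets, ECG | 71-98 | 84 | 3 | 28 | 28 - 7 = 21 |
| Week 16 | CK, troponin | 109-140 | 112 | 10 | 32 | 32 - 14 = 18 |
| Week 24 | all of these | 141-210 | 168 | 14 | 70 | 70 - 29 = 41 (59%) |
| Week 36 | all of these | 211-294 | 252 | 14 | 84 | 84 - 29 = 55 (65%) |
| Week 48 | all of these | 295-442 | 336 | 14 | 148 | 148 - 29 = 119 (80%) |
| Month 18 | all of these | 443-639 | 548 | 14 | 197 | 197 - 29 = 168 (85%) |

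CK windows are 7 days for Weeks 2 to 15. Troponin windows are 7 days at Weeks 2, 3 and 9 to 15. None of these has a day on which an unscheduled value must lose. The 18 days in the Week 16 row all fall after that visit (Days 123-140).

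**Example.** In the Week 24 window, take a scheduled troponin on Day 168 and an unscheduled one on Day 190. The distances are 0 and 22 days, so the Day 168 value is tabulated whatever the Day 190 level.

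**Late follow-up.** Protocol 5.6 schedules CK, liver tests and troponin at Months 72 to 120. As extracted, the Table 10 columns for CK/LFTs and for troponin end in an open Month 60 window (Day 1735 onward), while the column for other chemistry and hematology continues with annual windows. If that is the true layout, values at Days 1825, 2190, 2555, 2920, 3285 and 3650 share one window. The value nearest Day 1825 is kept, and the five annual visits after Month 60 drop out of the by-visit tables. The extraction may be at fault: the serum bile acid column shows both an open Month 60 window and later annual ones.

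**The case against.** The strongest reply is that peaks reach other outputs.

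- **Adverse events.** Under Protocol 6.3.1, a Grade 3 or 4 laboratory result worse than baseline is reported as an adverse event unless a reported diagnosis covers it. Protocol 6.4 requires recording of low platelets, and of raised troponin when work-up or treatment is indicated. SAP 4.6.1 tabulates Grade 3 or higher events by period, with separate muscle and myocarditis categories.
- **Grade shift.** This table is not by visit: "Grade 1 shift from baseline in laboratory test result will be summarized by dose level and laboratory parameter", counting rises of at least one grade. Protocol 7.4.1.2 counts such rises at any post-baseline time.
- **Listings.** All laboratory results are listed, with flags.
- **Early windows.** The thrombocytopenia in Protocol 1.5 arose within 2 weeks of dosing, where hematology windows last 4, 6 and 11 days.

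Much of this stands, and it limits the consequence without closing the gap. The shift table shows that a rise occurred, not how high it went, and the SAP omits the protocol's any-time wording. Values covered by a diagnosis, and troponin rises needing no work-up or treatment, need not become separate events. Listings are not summaries.

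A reader might infer that every safety threshold table loses peaks. The documents do not support that. The table of potentially clinically significant laboratory values is worded both ways: "a laboratory value meeting the threshold criteria during the investigational period will be summarized by dose level group and visit". Platelets have no criterion in that table, so they cannot drop out of it. The central-first rule is a laboratory rule and cannot touch ECG. Nor are liver tests the only domain with a peak rule, since vital signs have one too.

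**Conclusion.** The point holds for the by-visit out-of-range, CTCAE-grade and ECG-criteria tables. The loss falls mainly after Week 16 for CK and troponin, and from about Week 4 for creatinine, platelet count and ECG. Within the windows from Week 24 to Month 18, an unscheduled value is certain to be dropped on 59% to 85% of days.

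These shares assume that the scheduled sample exists and is within its visit tolerance. They describe days, not children. A reader might turn them into a proportion of missed peaks or missed children, for instance by treating each draw in a window as equally likely to be kept. The documents do not say how many unscheduled values exist, when they were taken or which laboratory ran them, so no such figure can be given. A dropped peak also need not change a child's category if the kept value falls in the same one.

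The Month 60 finding is conditional on the layout of Table 10. The table of potentially clinically significant values needs clarification rather than correction. The change is a cheap improvement worth making in a descriptive safety report.

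**What to change.** 1. Keep nearest-day and central-first selection for descriptive means by visit.
2. Add to the CTCAE-grade, out-of-range and ECG-criteria tables a worst post-baseline value for each of the four periods in SAP 4.6.2.2, the last of which is the whole study. Use all scheduled and unscheduled values. For laboratory tests, use central and local results, graded on the reporting laboratory's range.
3. State that the grade-shift table and the table of potentially clinically significant laboratory values use any post-baseline value.
4. Check Table 10, and add Month 72 to 120 windows for CK, liver tests and troponin if they are absent.
5. Add troponin I to the subject line plots in SAP 4.2.6.

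The cost is SAP wording and some added programming, with no new data collection. Reported abnormality frequencies will be higher.
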